TITLE: Daratumumab Infusion Acceleration

Center: The Ohio State University

Principal Investigator: [name] MD MPH
[name]
[name]
[name]
[contact] (voice); [contact] (fax)
[contact]

Co-Investigators: (patient-care)
[name] MD MPH
[name] MD PhD
[name]

Pharmacy: [name] PharmD BCOP

Statistician [name] PhD

Regulatory [name] BS

[figure not shown]
Data coordination [name] PhD

Commercial Agent: Daratumumab

Protocol / Version / Date: Original / v1.1 / 26-Aug-2016

SCHEMA

Title:	Daratumumab Infusion Acceleration
Objectives:	Determine the safety and tolerability of decreasing the infusion time of daratumumab in patients that have already received 2+ doses of daratumumab and are continuing on Daratumumab Estimate the time savings vs predicted infusion time
Population:	Any patient receiving daratumumab
Phase:	2
Number of sites:	1
Description of treatment :	Interventional unblinded Simon two-stage design of a faster Daratumumab infusion in patients who have received ≥ 2 infusions.
Study duration:	12-24 months
Participant duration:	Maximum 3 months

Starting with dose #3 or later of Daratumumab, we propose to infuse approximately 20% over 30 minutes, then 80% over 60 minutes, total duration of 1.5 hours, saving an estimated 2 hours.

Daratumumab Infusion Rates					
Dose	Total Volume ¹	Initial Rate	Rate Increment	Max Rate	Time ²
Standard of care dose ≥ 3	550 mL	100 mL/hr	50 mL/hr every 1 hr	200 mL/hr	3.5 hr
Investigational dose ≥ 3	550 mL	200 mL/hr	30 minutes	450 mL/hr	1.5 hr

¹Includes estimated overfill; ²Estimated

TABLE OF CONTENTS

SCHEMA.....	2
TABLE OF CONTENTS	3
1. LIST OF ABBREVIATIONS	4
2. STATEMENT OF COMPLIANCE	4
3. KEY ROLES.....	4
4. OBJECTIVES.....	5
5. BACKGROUND.....	5
5.1 MULTIPLE MYELOMA	5
5.2 RATIONALE	6
6. PATIENT SELECTION	8
6.1 ELIGIBILITY CRITERIA	8
6.2 EXCLUSION CRITERIA.....	8
7. REGISTRATION PROCEDURES.....	9
7.1 GENERAL GUIDELINES	9
8. TREATMENT PLAN.....	9
8.1 AGENT ADMINISTRATION	9
8.2 PREMEDICATION.....	9
8.3 MONITORING.....	9
8.4 DURATION OF THERAPY.....	10
8.5 DURATION OF FOLLOW-UP.....	10
8.6 CRITERIA FOR REMOVAL FROM STUDY	10
9. DOSING DELAYS / DOSE MODIFICATIONS	10
9.1 GRADE 1-2 INFUSION RELATED REACTIONS	10
9.2 GRADE 3 INFUSION RELATED REACTION	10
9.3 GRADE 4 INFUSION RELATED REACTION	10
10. PHARMACEUTICAL INFORMATION.....	10
10.1 DARATUMUMAB	11
10.2 DEXAMETHASONE	11
11. STUDY CALENDARS	12
11.1 SCHEDULE OF EVENTS	12

1. LIST OF ABBREVIATIONS

AE	Adverse event
BP	Blood pressure
CRF	Case Report Form
DSMB	Data Safety Monitoring Board
eCRF	Electronic Case Report Form
FDA	Food and Drug Administration
GCP	Good Clinical Practice
GLP	Good Laboratory Practices
GMP	Good Manufacturing Practices
HIPAA	Health Insurance Portability and Accountability Act
HR	Heart rate
IB	Investigator's Brochure
IND	Investigational New Drug Application
IRB	Investigational Review Board
IRR	Infusion Related Reaction
IV	Intravenous
NIH	National Institutes of Health
PI	Principal Investigator
PO	By mouth
RR	Respiratory rate
SAE	Serious Adverse Event
SOP	Standard Operating Procedure
US	United States

4. OBJECTIVES

Hypothesis	Objective	Endpoint
Infusing daratumumab will not be associated with any grade 3-4 infusion related reactions	Determine the safety and tolerability of decreasing the infusion time of daratumumab in patients that have already received 2+ doses of daratumumab and are continuing on Daratumumab	Analysis of AEs possibly, probably, or definitely related to protocol therapy will summarize infusion related grade 3-4 reactions.
Accelerated daratumumab infusion will significantly decrease the time patients spend waiting for daratumumab to infuse.	Estimate the time savings vs predicted infusion time	The start and stop times of daratumumab infusion will be tracked during infusion acceleration and the number of daratumumab infusions will be tracked from the time of consent until the last daratumumab infusion.

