8. TREATMENT PLAN

8.1 Agent administration

Treatment will be administered on an outpatient basis.

Starting with dose #3 or later of daratumumab 16 mg/kg IV, we will infuse approximately 20% over 30 minutes, then 80% over 60 minutes, total duration of 1.5 hours, saving an estimated 2 hours. The initial rate will be 200 mL/hr (30 mins) and then 450 mL/hr (60 mins).

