8.4 Duration of therapy

All further doses of daratumumab may be administered as described in section 8.1, however patient will be considered “off-study” after the pre-defined follow-up period.

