8.5 Duration of follow-up

Patients will be followed for 4 weeks from the first accelerated infusion.

Patients removed from study for unacceptable adverse event(s) will be followed until resolution or stabilization of the adverse event.

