11. STUDY CALENDARS

Patients will be approached in the infusion suite for consent, generally within 4 weeks of day 1. Screening and first infusion can occur on the same day.

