11.1 SCHEDULE OF EVENTS

Assessment	Screening	First accelerated infusion
Signed informed consent	X	
Inclusion/Exclusion Criteria	X	
Height and weight ^a	X	
Vital signs	X	X
Daratumumab administration		X
Record adverse events		X

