12. STATISTICAL CONSIDERATIONS

12.1 General approach

The primary objective of this study is to assess the safety of administering Daratumumab over a shortened period of time following the first two standard doses. The primary endpoint is infusion-related reactions (IRR) assessed with the first dose using the accelerated dosing regimen. The incidence rate of IRR is defined and calculated as the number of patients with grade 3 IRR divided by the total number of patients who receive the accelerated dosing regimen.

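### Does counting infusions from consent to the last infusion, while timing only the accelerated ones, distort the time-saving estimate?

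*Combined protocol and SAP*

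**What the plan says.** Section 4 lists two objectives. The second is to estimate the time saved against a predicted infusion time, and its endpoint has two parts. In the first, the "start and stop times of daratumumab infusion will be tracked during infusion acceleration". In the second, the "number of daratumumab infusions will be tracked from the time of consent until the last daratumumab infusion".

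Other sections set the limits of these two windows:

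- **Consent.** Section 11 states: "Patients will be approached in the infusion suite for consent, generally within 4 weeks of day 1". It also allows screening and the first infusion on one day.
- **Follow-up.** Section 8.5 states: "Patients will be followed for 4 weeks from the first accelerated infusion". Section 8.4 states: "All further doses of daratumumab may be administered as described in section 8.1", with the patient then off study. The Schema caps participation at three months.
- **Calendar.** The last column of the table in Section 11.1 is "First accelerated infusion". Section 8.3 nevertheless describes monitoring at later accelerated infusions, and the Appendix B nurse form has fields for start and end time.
- **Expected saving.** Section 8.1 gives a "total duration of 1.5 hours, saving an estimated 2 hours". The Schema sets an estimated 3.5 hours for the standard infusion beside 1.5 hours for the accelerated one.
- **Analysis.** Section 12.1 states: "The primary endpoint is infusion-related reactions (IRR) assessed with the first dose using the accelerated dosing regimen". Nothing in Section 12 describes an analysis of infusion time.

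**The concern.** The two halves of one endpoint cover different sets of infusions. Timing is confined to accelerated infusions. The count starts at consent, when a patient may still be receiving standard-rate infusions, and runs to a last infusion that may come after the patient has left the study. A natural use for a count under a time-saving objective is to scale a saving per infusion up to a total per patient. A total built that way would credit two hours to infusions that saved nothing, and would add infusions outside follow-up.

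The plan also does not name the predicted time in the endpoint itself. It gives no summary measure or interval, although the hypothesis in Section 4 speaks of a significant decrease. What is at stake is the credibility of the second objective, in particular any headline figure for hours saved per patient.

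**Working it through.** **1. The plan's own figure.** Inputs are from the Schema and Section 8.1, for 550 mL.

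- Standard: 100 mL in hour 1 + 150 mL in hour 2 = 250 mL. The remaining 300 mL at 200 mL/hr takes 300/200 = 1.5 h. Total 2 + 1.5 = 3.5 h.
- Accelerated: 200 × 0.5 + 450 × 1.0 = 100 + 450 = 550 mL in 1.5 h.
- Saving: 3.5 − 1.5 = 2.0 h. The stated 2 hours is reproduced.

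**2. How far a count-based total could go wrong within follow-up.** The dosing frequency is from Section 5.2: eight weekly doses, eight every other week, then monthly. Assumptions:

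- A month is 28 days, and day 1 is the first accelerated infusion.
- Consent falls up to 28 days earlier, and an infusion on the consent day is counted.
- Only doses from #3 on can precede acceleration, because eligibility needs two earlier infusions.
- The count stops at the four-week follow-up, and 2 h is credited per counted infusion.

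Section 5.2 does not give the interval between doses #8 and #9, so both 7 and 14 days are shown where it matters.

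| First accelerated dose | Standard-rate infusions counted | Accelerated in 4 weeks | Count × 2 h | Accelerated × 2 h | Excess |
|---|---|---|---|---|---|
| #3 | 0 | 5 | 10 | 10 | 0% |
| #6 | 3 | 4 | 14 | 8 | 75% |
| #7 (14 days) | 4 | 3 | 14 | 6 | 133% |
| #7 (7 days) | 4 | 4 | 16 | 8 | 100% |
| #10 (14 days) | 2 | 3 | 10 | 6 | 67% |
| #10 (7 days) | 3 | 3 | 12 | 6 | 100% |
| #18 | 1 | 2 | 6 | 4 | 50% |

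With same-day consent the standard-rate column is zero in every row and the excess vanishes.

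**3. Beyond follow-up.** Take first accelerated dose #7, consent 28 days earlier, the 7-day interval, and a last counted infusion 13 weeks after the first accelerated one. The count is 4 standard-rate + 4 accelerated on study + 4 off study = 12, so 12 × 2 = 24 h. On-study accelerated infusions give 4 × 2 = 8 h. If the off-study doses were also accelerated, the true saving is (4 + 4) × 2 = 16 h.

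The Schema's three-month maximum and the four-week follow-up do not contradict each other. Four weeks of lead time plus four weeks of follow-up is eight weeks, inside the maximum.

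**4. Whether the plan leads there.** The objective is a saving against predicted time, so each infusion contributes predicted minus observed. An accelerated infusion contributes nominally 3.5 − 1.5 = 2.0 h. A standard-rate infusion, if someone included it, contributes nominally 3.5 − 3.5 = 0 h. Summing what is actually timed therefore gives the fifth column of the table, not the fourth. The excess arises only from count times 2 h, and no section states that formula.

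**The case for a change.** The best case for a change is that time saving is one of only two objectives, with a hypothesis of a significant decrease, and yet it has no estimator, interval or analysis set. Two analysts could choose different windows and report very different hours per patient from the same records. A few words in Section 4 and a sentence in Section 12 would prevent that at almost no cost.

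Part of this stands. The windows do differ, Section 12 is silent, and the calendar in Section 11.1 stops at the first accelerated infusion although Section 8.3 looks further.

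The rest is weaker. The comparator is in practice supplied: the Schema sets 3.5 hours beside 1.5, and Section 8.1 repeats the difference. I could not read the institutional infusion table in Section 5.2, so nothing here depends on what it contains. Leaving standard-rate infusions untimed is no defect when the comparison is with a predicted time. The last infusion is most naturally read as the last one on study, since Section 8.4 closes participation after follow-up and the Schema caps it at three months. The large percentages need a consent gap that Section 11 permits but does not require, and they shift with an interval the plan leaves open.

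**Conclusion.** No change is needed. The mismatch in wording is real, but it would bias only a cumulative total that the plan does not define: by 0% to 133% in the four-week cases above, and by 24 h against 8 h (or 16 h) in the 13-week case. Those figures assume consent as early as 28 days before the first accelerated dose and a flat 2 h credited to every counted infusion. With same-day consent and the last infusion inside four weeks, the two totals agree.

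The quantity the objective asks for, the saving per accelerated infusion against the standard 3.5 hours, is unaffected and can be estimated from the times on the Appendix B form. An analyst would report predicted minus observed time for the infusions that were timed, and would not credit savings to infusions given at the standard rate. The primary safety endpoint, the two-stage decision rule and the sample of 28 make no use of infusion time. Writing the window, the comparator and the summary into the plan would be tidy, but it would not alter the result that the trial is set up to give.

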5. BACKGROUND

5.1 Multiple myeloma

Multiple myeloma (MM) affects approximately 83,000 US citizens and over 50% of patients die within 5 years of diagnosis; more than half of patients older than 70 years with low albumin and high β 2microglobulin die within a year of diagnosis^{1,2}. Of the 30,330 new cases estimated in 2016 in the U.S.³, is twice as common in African Americans as Caucasians, and genetic changes accumulate as plasma cells degenerate from monoclonal gammopathy of undetermined significance, through smoldering myeloma, to MM⁴. MM is characterized by fractures, anemia, kidney failure, and hypercalcemia with a predisposition for bacterial infections from the inherent immunoparesis and varicella reactivation often aided by proteasome inhibition⁵.

Patients have been treated with combinations of cereblon-binding drugs (e.g. immunomodulatory drugs [IMiD's] thalidomide, lenalidomide, pomalidomide), proteasome inhibitors (e.g. bortezomib, carfilzomib), and dexamethasone. MM cells are strongly dependent on the BM microenvironment (e.g. bone marrow stromal cells,

endothelial cells, osteoclasts) via the production of supportive growth factors. Moreover MM cells are able to escape immune surveillance by creating an immunosuppressive BM microenvironment favorable to their survival.

[figure not shown]
Two antibodies have received FDA approval in 2015 for relapsed refractory disease: elotuzumab (HuLuc63) is a humanized immunoglobulin (Ig)G1-k antibody targeting signaling lymphocytic activation molecule F7 (SLAMF7, CS1 [CD2 Subset 1]), and daratumumab (HuMax-CD38) is an immunoglobulin G1 kappa (IgG1κ) human monoclonal antibody that binds a CD38 epitope.

5.2 Rationale

In SIRIUS, after diphenhydramine 25-50 mg, acetaminophen 650-1000 mg, and methylprednisolone 100 mg intravenously, infusion-related reactions occurred in 45 (42%) patients and were predominantly grade 1 or 2 (grade 3 occurred in five [5%] patients). Thirty-seven percent of patients experienced infusion-related reactions during the first infusion and only six (6%) patients had more than one infusion-related reaction. The most common ($\geq 5\%$) infusion-related reactions included nasal congestion (13 [12%]), throat irritation (seven [7%]), and cough, dyspnea, chills, and vomiting (six [6%] each). In the dose-escalation study⁶, the frequency of infusion-related reactions was lower among patients who received 8 mg/kg in 1000 mL for 6 hours than among those who received 8 mg/kg in 500 mL for 4-6 hour or 16 mg/kg in 1000 mL for 6 hours, all suggesting that the infusion rate factors into infusion reactions. **All IRRs can be considered non-life threatening according to CTCAE grading system, most being nasal congestion.**

[figure not shown]
For patients receiving commercial daratumumab now, if a patient suffers grade 1-2 infusion reactions, we interrupt daratumumab. When symptoms resolve, we start at the last tolerated rate for one hour and begin re-escalating the infusion rate as tolerated. For grade 3 infusion reaction, we stop the infusion, treat medically, and restart at half the rate when symptoms improve to grade 0-1. The first dose of daratumumab should be diluted in one liter, but if this is well-tolerated, subsequent infusions can be diluted in 500 mL. Daratumumab is approved for 8 weekly infusions, 8 every other week infusions, and then monthly thereafter until progression. Our current institutional infusion recommendations for commercial daratumumab are shown below.

Daratumumab Infusions – Institution Standard

**Montelukast typically discontinued after dose #3.

This protocol focuses on dose #3 or later, when the risk of grade 3-4 infusion related reactions was very small in trials reported to date, as shown in the figure below.

6. PATIENT SELECTION

6.1 Eligibility criteria

- 6.1.1 Patients must have received ≥ 2 daratumumab infusions and be scheduled to receive another dose.
- 6.1.2 Both men and women of all races and ethnic groups are eligible for this study.
- 6.1.3 Age ≥ 18 years. Because no dosing or adverse event data are currently available on the use of daratumumab in patients <18 years of age, children are excluded from this study.
- 6.1.4 Ability to understand and the willingness to sign a written informed consent document.

6.2 Exclusion Criteria

- 6.2.1 Any other medical condition, including mental illness or substance abuse, deemed by the principal investigator to likely interfere with a patient's ability to sign informed consent, cooperate and participate in the study, or interfere with the interpretation of the results.
- 6.2.2 Concurrent use of complementary or alternative medicines that in the opinion of the principal investigator would confound the interpretation of toxicities and/or antitumor activity of the study drug
- 6.2.3 Prisoner

7. REGISTRATION PROCEDURES

7.1 General Guidelines

Eligible patients will be entered on study at Ohio State University by [name].

8. TREATMENT PLAN

8.1 Agent administration

Treatment will be administered on an outpatient basis.

Starting with dose #3 or later of daratumumab 16 mg/kg IV, we will infuse approximately 20% over 30 minutes, then 80% over 60 minutes, total duration of 1.5 hours, saving an estimated 2 hours. The initial rate will be 200 mL/hr (30 mins) and then 450 mL/hr (60 mins).

8.2 Premedication

The following premedications are recommended approximately 1 hour prior to daratumumab infusion per the package insert:

- Dexamethasone 12 - 20 mg IV/PO
- Diphenhydramine 25 - 50 mg IV/PO
- Acetaminophen 650 mg PO

The OSU institutional standard for infusion #3 and onward is

- Dexamethasone 12-20 mg IV/PO
- Famotidine 20 mg IV/PO
- Montelukast 10 mg PO (typically discontinued after dose #3)
- Consider acetaminophen 325-650 mg PO
- Consider diphenhydramine 12-25 mg IV/PO

If the premedication regimen has been adjusted due to prior tolerability or physician preference, the appropriateness of the premedication regimen will be evaluated by the study team.

8.3 Monitoring

Vital signs (HR, BP, temp, RR) will be taken just prior to infusion start, then every 15 minutes for the first hour of infusion, then lastly at the end of infusion (see Appendix B monitoring form). Patient will remain in the infusion clinic for a 30-minute post observation period after the first accelerated infusion *only*. If the infusion is well-tolerated, subsequent vital sign monitoring will occur prior to infusion start, at rate increase, and lastly at the end of infusion. Patients will be educated on the signs of

delayed infusion reaction and instructed to contact physician for any issues after discharge from clinic.

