8.6 Criteria for removal from study

If the patient suffers a grade 4 infusion reaction, the patient will be removed from the study.

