9.1 Grade 1-2 infusion related reactions

At the time that this protocol was written, for daratumumab grade 1-2 infusion reactions, interrupt daratumumab. When symptoms resolve, start at the last tolerated rate for one hour and begin re-escalating the infusion rate as tolerated.

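### Section 8.3 ties the vital-sign step-down to tolerance but requires the 30-minute post-infusion stay at the first accelerated infusion only, so a patient who reacted has no protocol-required stay after the next one

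*Combined protocol and SAP*

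**What the plan says.** Section 8.3 sets two monitoring rules side by side.

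- Post-infusion stay: a "30-minute post observation period after the first accelerated infusion *only". The word 'only' is emphasised in the protocol, and tolerance is not mentioned.
- Vital signs: at the first accelerated infusion, before the start, then "every 15 minutes for the first hour of infusion, then lastly at the end of infusion". The lighter schedule that follows is conditional: "If the infusion is well-tolerated, subsequent vital sign monitoring will occur prior to infusion start", at the rate increase and at the end.

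Section 8.3 also has patients taught the signs of a delayed reaction and told to call a physician.

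Other sections determine who can reach a second accelerated infusion on study.

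- Section 8.4: "All further doses of daratumumab may be administered as described in section 8.1". This is permission, not a requirement.
- Section 8.5: "Patients will be followed for 4 weeks from the first accelerated infusion". It adds that "Patients removed from study for unacceptable adverse event(s) will be followed until resolution or stabilization of the adverse event", without defining which events are unacceptable.
- Section 8.6, the only defined removal criterion: "If the patient suffers a grade 4 infusion reaction, the patient will be removed from the study".
- Section 9.1, for grade 1-2 reactions: interrupt, then "When symptoms resolve, start at the last tolerated rate for one hour and begin re-escalating the infusion rate as tolerated".
- Section 9.2, for grade 3 reactions: follow institutional protocol, which is summarised as stop, treat, and restart at half rate.

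**The concern.** Section 8.3 accepts that a patient's experience of the accelerated infusion should decide how closely the next one is watched, but applies this to vital signs and not to the stay. Section 5.2 argues that infusion rate contributes to reactions, and 8.3 itself anticipates delayed ones. A patient who has already reacted at the faster rate is the one for whom a further half hour in clinic is most relevant. As written, a reaction that begins after the end of that patient's next accelerated infusion would be seen in clinic only if a clinician chose to keep the patient there. What is at stake is the safety of a few patients, not the validity of the trial's conclusion.

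**Working it through.** **1. Does any other section require the stay?**

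- 8.4 allows further accelerated doses.
- 8.6 removes grade 4 reactors only, so no defined criterion takes a grade 1-3 reactor off study.
- 9.1 and 9.2 deal with the infusion in progress. Neither sets observation after the next one.
- The schedule in 11.1 has columns for screening and the first accelerated infusion only.
- The Appendix B form ends at end of infusion.

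No visible text requires a stay after a second or later accelerated infusion. For vital signs, a patient whose infusion was not well tolerated does not meet the condition for the step-down. By implication that patient keeps the 15-minute checks in the first hour and the end-of-infusion check.

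**2. How many infusions are exposed?**

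Inputs are 28 days of follow-up (8.5) and 8 weekly doses, 8 two-weekly doses, then monthly (5.2). Assumptions not in the documents: no dosing delays, monthly taken as 28 days, a gap of 7 or 14 days from dose 8 to 9, and a gap of 14 or 28 days from dose 16 to 17. The lower figure leaves out a dose falling on day 28 and the upper includes it.

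| First accelerated dose | Further doses in follow-up |
|---|---|
| #3 to #5 | 3-4 |
| #6 to #7 | 2-3 |
| #8 to #15 | 1-2 |
| #16 or later | 0-1 |

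For example, from dose #3 the next doses fall on days 7, 14, 21 and 28, giving 3 or 4. From dose #17 the next falls on day 28, giving 0 or 1. These count possible doses per patient; they do not count reactions.

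**3. Who would be affected?**

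Under 12.2 the regimen is declared too toxic at 2 or more grade 3 reactors among 28. A successful trial therefore has at most 1, and any other affected patients would be grade 1-2 reactors.

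**4. What would a repeated stay cost?**

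The plan's own saving reproduces: 200 mL/hr x 0.5 hr + 450 mL/hr x 1 hr = 100 + 450 = 550 mL in 90 minutes. Standard time is 3.5 hr = 210 minutes, so the saving is 210 - 90 = 120 minutes.

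- Uninterrupted later infusion: 120 - 30 = 90 minutes left; the stay takes 30/120 = 25% of the saving.
- Reaction at 30 minutes, patient kept at 200 mL/hr: 450 mL remain, taking 450/200 x 60 = 135 minutes. The total is 30 + 135 = 165, the saving 210 - 165 = 45, and 45 - 30 = 15 minutes are left, less the interruption.
- Reaction at 30 minutes, one hour at 200 mL/hr, then straight to 450 mL/hr: 250 mL remain after that hour, taking 250/450 x 60 = 33.3 minutes. The total is 30 + 60 + 33.3 = 123.3, the saving 86.7, and 56.7 minutes are left, less the interruption.

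Section 9.1 says to re-escalate as tolerated, so either interrupted case is possible. No figure is given for a grade 3 restart, because 9.2 leaves later escalation to the physician.

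**5. Is the design touched?**

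No. The endpoint in 12.1 is assessed at the first accelerated dose, when the stay is mandatory. The design figures in 12.2 also reproduce exactly:

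- Early stopping at a safety rate of 0.85: 1 - 0.85^7 = 0.679 (stated 68%).
- Type I error: 0.85^7 x (0.85^21 + 21 x 0.15 x 0.85^20) = 0.0497 (limit 0.05).
- Power: 0.98^7 x (0.98^21 + 21 x 0.02 x 0.98^20) = 0.811 (stated 80%).

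None of these depends on the stay at later infusions.

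**The case against.** The strongest reply is that this is a deliberate choice. The emphasis on 'only' suggests so, the stay matches the scope of the endpoint and schedule, and two monitoring measures need not share a trigger. The sentence says where a stay is mandatory; it does not forbid one elsewhere. Section 9.2 defers to institutional protocol, section 10 refers to the package inserts, and the institutional table in 5.2 cannot be read in the text supplied, so a stay after a prior reaction may already be required in practice. What remains is narrow: a grade 1-3 reactor, re-treated at the faster rate within 4 weeks, whose symptoms begin after the infusion ends, and whose clinician did not keep the patient.

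Most of this stands, and it is why the point is minor. It does not explain why reactors are treated like patients who tolerated the infusion for the stay, when the next sentence of 8.3 separates the two groups for vital signs.

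A reader might also take the SIRIUS figures in 5.2 (45 patients with a reaction, 6 with more than one: 6/45 = 13%) as the chance of recurrence at the next accelerated infusion. The documents do not support that. The figure is from standard rates, covers reactions of any timing, and is not said to refer to successive infusions.

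**Conclusion.** The point holds as a minor inconsistency in patient-safety monitoring. In the visible text, a grade 1-3 reactor re-treated on the accelerated schedule during follow-up has no required post-infusion stay, over 0 to 4 further infusions under the dosing-gap assumptions above. The size of any harm cannot be given, because the documents report no rate for reactions after the end of a later infusion.

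Three stronger readings should be resisted.

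- That prior reactors go unmonitored: patients who do not qualify for the step-down keep the fuller vital-sign schedule, and education and clinician discretion apply. Section 8.3 does not define well tolerated, so which grades keep that schedule is for the investigators to state.
- That the safety result or adverse-event capture is compromised: the endpoint belongs to the first accelerated dose, and 11.1 schedules adverse-event recording only there.
- That the site has no rule on this: the institutional standard could not be read.

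**What to change.** In 8.3, require the 30-minute stay after the first accelerated infusion and after each later accelerated infusion during follow-up until one has been well tolerated, with the investigators stating the grade that defines this. If the institutional standard already requires a stay after a prior reaction, cite it in 8.3 and delete 'only'.

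The change is one clause, with no effect on sample size, decision rules or analysis. It adds about 30 minutes per affected infusion, for prior reactors only, and at most 4 x 30 = 120 minutes per patient over follow-up. After an interrupted infusion the time saving left may be small, but most of that loss comes from the reaction and the slower restart; the stay itself still adds 30 minutes.
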